## 1.0 TRIAL SUMMARY

Abbreviated Title	Pembrolizumab (MK-3475) and radiation for relapsed and refractory Non-Hodgkin Lymphoma
Trial Phase	II
Clinical Indication	Refractory Non-Hodgkin Lymphoma
Trial Type	Treatment (Interventional)
Type of control	Historical Control
Route of administration	Intravenous and external beam radiation
Trial Blinding	Unblinded, open label
Treatment Groups	MK-3475 200 mg every 21 days with concurrent External beam radiation therapy (EBRT)
Number of trial subjects	21
Estimated enrollment period	20 months
Estimated duration of trial	48 months
Duration of Participation	1.5 years
Estimated average length of treatment per patient	24 months

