### 3.0 OBJECTIVES & HYPOTHESES

#### 3.1 Primary Objective & Hypothesis

- 1) **Primary Objective:** To determine the overall response rate (ORR) of pembrolizumab with concurrent fractionated EBRT among patients with relapsed and refractory NHL.

**Hypothesis:** Therapy with pembrolizumab concurrent with EBRT will result in an ORR of at least 35% in unirradiated lesions among patients with relapsed and refractory NHL and roughly 90% among patients with relapsed and refractory NHL treated comprehensively to all sites of radiographically apparent disease that can be encompassed in 1-2 radiation therapy fields.

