*PD-1 blockade for lymphoma.* Manipulation of the PD-1/PDL-1 pathway is of recent interest in patients with classical Hodgkin lymphoma (cHL) and several non-Hodgkin lymphomas (NHLs) including follicular lymphoma (FL) and diffuse large B-cell lymphoma (DLBCL). Indeed in cHL, two distinct phase 1 clinical trials evaluating single agent PD-1 blockade with a monoclonal antibody demonstrated impressive overall response rates (ORR) of 87% and 53% among patients with refractory cHL, of whom the majority failed autologous stem cell transplantation as well as brentuximab. Complete response (CR) rates were 17% and 20% in these studies. Data is also emerging regarding the clinical utility of immune checkpoint inhibition in NHL. We have recently demonstrated that in FL, PD-1 blockade in combination with anti-CD20 targeting agent rituximab was well tolerated and resulted in an ORR of 66% and CR in 52% of patients treated with this approach. A recent publication in *Blood* revealed that among patients with DLBCL, tumor biopsy expression of PD-L1 negatively impacted overall survival suggesting a potential role for the PD-1/PD-L1 pathway in this patient population.

Preliminary data from an ongoing trial evaluating PD-1 blockade in NHLs, however suggests that the full potential of immune checkpoint blockage will not be reached with anti-PD-1 monotherapy. In this study of 81 patients, including 31 and 23 patients with B-cell NHL and T-cell NHL respectively, the ORR was 26% among patients with B cell NHL and 17% among patients with T-cell NHL (Figure 3). The compete response rate was 10% among the B cell NHL subjects and 0% for those with T cell NHL. This suggests that effective cancer immunotherapy likely requires cooperation with other anti-tumor modalities for improved

efficacy. One potential combination strategy to augment response is external beam radiation therapy coupled with PD-1 blockade.

Tumor	OR, No. (%)	CR, No. (%)	PR, No. (%)	SD, No. (%)	Median PFS, Weeks (95% CI)
B-cell lymphoma (n = 31)	8 (26)	3 (10)	5 (16)	16 (52)	23 (7 to 44)
DLBCL (n = 11)	4 (36)	2 (18)	2 (18)	3 (27)	7 (6 to 29)
FL (n = 10)	4 (40)	1 (10)	3 (30)	6 (60)	NR (7 to NR)
Other B-cell lymphoma (n = 10)	0	0	0	7 (70)	11 (3 to 39)
T-cell lymphoma (n = 23)	4 (17)	0	4 (17)	10 (43)	10 (7 to 33)
MF (n = 13)	2 (15)	0	2 (15)	9 (69)	10 (7 to 35)
PTCL (n = 5)	2 (40)	0	2 (40)	0	14 (3 to NR)
Other CTCL (n = 3)	0	0	0	0	7 (6 to NR)

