It is likely that the timing of immune checkpoint blockade and EBRT influence the effectiveness of therapy. In a pre-clinical model of melanoma, breast and colorectal cancer, the anti-tumor activity of low dose fractionated RT was enhanced through the combination of a monoclonal antibody targeting PD-L1. In this mouse model, treatment timing and scheduling was significantly affected treatment efficacy; with concurrent RT and PD-L1 therapy but not sequential therapy resulting in beneficial local control and survival. Based on these data we propose that pembrolizumab and fractionated RT should be administered concurrently.

The overall response rates of refractory NHL to single modality radiation therapy are relatively high but often not durable. In a retrospective study from the Dana-Farber Cancer Institute of 110 patients treated with a course of salvage radiation therapy for relapsed or refractory aggressive NHL, the overall response rate was 78% among refractory patients treated with curative intent and 81% for those refractory patients treated with palliative intent. Among living patients the 5 year rate of progression free survival however was only 34%. Furthermore even among patients treated with doses greater than 40 Gy with curative intent the 2 year local control rate was only 61%. This highlights 1) the need for effective systemic therapies to pair with salvage radiation therapy and 2) the room for improvement in long term local control that for patients with refractory NHL that may be accomplished with concurrent systemic therapy.

Given this data this study will address the role of pembrolizumab and concurrent RT in two patient populations. The first eligible cohort will include patients with more disseminated disease where all disease will not be included in the radiation field and there will be an “unirradiated lesion”. The second cohort of eligible patients will be those with relapsed/refractory aggressive NHL where all sites of disease can be encompassed in 1-2 radiation therapy fields. We hypothesize that 1) the response rates of the unirradiated lesion will be higher than reported ORR among patients treated previously with PD-1 blockade monotherapy for relapsed and refractory NHL and 2) the response rates for patients treated

with pembrolizumab and RT fields encompassing all sites of disease will be also be improved over rates reported for salvage RT alone.

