### **8.0 STATISTICAL ANALYSIS PLAN**

#### **8.1 Statistical Analysis Plan Summary**

This is an investigator initiated, open label, phase II clinical trial to evaluate the efficacy of the combination therapy of Pembrolizumab and fractionated external beam radiotherapy (EBRT) in patients with relapsed and refractory aggressive Non-Hodgkin lymphoma (NHL). The maximum number of patients that will be recruited for the study is 40.

The primary objective of the trial is to determine the overall response rate of Pembrolizumab and fractionated EBRT in patients with relapsed and refractory NHL. The secondary objectives are to evaluate the safety, CRR, PFS, OS and duration of response of pembrolizumab with concurrent fractionated EBRT. Patients will receive 200 mg IV of Pembrolizumab with concurrent EBRT at standard of care doses of 40-50 Gy of EBRT in fractions of  $\leq 3$  Gy.. The trial enrollment will be stratified according to the extent of relapsed/refractory disease included in the RT field(s) with 2 cohorts of patients enrolled based on the treated RT field. For Cohort 1, patients with aggressive NHL, will receive RT to 1-2 region(s) of disease and the ORR will be determined for a designated “unirradiated” lesion (Cohort 1). For patients with relapsed/refractory aggressive NHL in Cohort 2, RT will be administered to encompass all sites of radiographically evident disease in 1-2 RT plan(s), the ORR will be based on the disease treated within the RT field. **The maximum number of patients in each cohort is 20 with a total anticipated trial enrollment of 40 patients..**

Overall response rates to PD-1 blockade monotherapy among patients with hematologic malignancies is based on published data. For cohort 1, we assume that concurrent external beam radiation therapy with concurrent pembrolizumab will improve ORR (of the non-irradiated lesion[s]) over the reported rates of PD-1 blockade which are roughly 26% for B cell lymphoma and 17% for T cell lymphoma.

**While the ORR for definitive RT for patients with de novo aggressive NHL approach 100%, overall response rate to salvage RT for patients with refractory aggressive NHL treated with curative intent has been reported to be 78%, with a 5 year progression free survival rate of 34%. We assume that concurrent EBRT and pembrolizumab will improve the ORR when all sites of known disease are radiated.**

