#### **8.2 Statistical Analysis Plan**

Phase II design:

The overall response (OR: complete response + partial response) of non-irradiated lesion(s) at three months and dose limiting toxicity (DLT) at one cycles (3 weeks) will be monitored simultaneously using the Bayesian stopping boundaries calculated based on beta-binomial distributions. Independence is assumed between OR and DLT.

DLT is defined as the following toxicities observed during cycle one of the treatment that are considered by the investigator to be related to therapy:

1. Grade 4 neutropenia (ANC < 500/mm3) lasting more than 7 consecutive days.
2. Grade 3 neutropenia with fever and/or infection, where fever is defined as an oral Temperature  $\geq 38.5^{\circ}\text{C}$ .
3. Grade 4 thrombocytopenia (platelets < 25,000/mm3) lasting more than 7 consecutive Days.
4. Grade 3 thrombocytopenia with clinically significant bleeding.
5. A platelet count < 10,000/mm3 at any time.
6. Grade 3 or greater nausea and/or emesis despite the use of optimal anti-emetic Prophylaxis. Optimal anti-emetic prophylaxis is defined as an anti-emetic regimen that employs a 5-HT3 antagonist given in standard doses and according to standard schedules.
7. Grade 3 or greater diarrhea that occurs despite maximal supportive therapy.
8. Any other Grade 3 or greater non-hematologic toxicity with the following exceptions: Grade 3 arthralgia/myalgia or brief (< 1 week) Grade 3 fatigue.
9. A delay of more than 2 weeks in the initiation of Cycle 2 of treatment because of a lack of adequate recovery of therapy related hematological or non-hematologic toxicities.

In cohort 1 for the patients with multiple sites of aggressive NHL, we will consider that the regimen is promising if the OR rate of the non-irradiated lesion (s) at 3 months is at least 35% and the DLT rate at cycle one is below 30%. A sample size of 20 ensures that, if the trial is not terminated early, a posterior 90% credibility interval for OR rate at 3 months will have width of 0.335 at most, when 7 responses are observed out of the 20 patients, under the assumption of 35% OR rate. The prior probability of OR and DLT for the regimen are modeled by beta distribution ( $\text{Beta}(0.35, 0.65)$  and  $\text{Beta}(0.3, 0.7)$ , respectively). Denoting the probability of OR and DLT by  $\{\theta_{\text{OR}}, \theta_{\text{DLT}}\}$ , and they are compared to fixed targets of OR and DLT rates. The following decision criteria will be applied:

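### The 26% anti-PD-1 reference for Cohort 1 counts follicular lymphoma patients whom the trial excludes, and the cohort labels in 5.3 conflict with 5.1.2 and 8.1 on T-cell lymphoma

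*Combined protocol and SAP*

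**What the plan says.** Section 1.0 gives the type of control as "Historical Control". Section 4.2.1 hypothesises that "the response rates of the unirradiated lesion will be higher than reported ORR among patients treated previously with PD-1 blockade monotherapy", and 8.1 assumes that adding radiation will improve response "over the reported rates of PD-1 blockade which are roughly 26% for B cell lymphoma and 17% for T cell lymphoma". The hypothesis in 3.1 is that treatment "will result in an ORR of at least 35% in unirradiated lesions among patients with relapsed and refractory NHL". Section 8.2 turns this into a criterion: "we will consider that the regimen is promising if the OR rate of the non-irradiated lesion (s) at 3 months is at least 35" per cent, together with a DLT rate below 30%. For monitoring, the OR and DLT probabilities are modelled and "they are compared to fixed targets of OR and DLT rates".

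The source of the 26% and 17% is the Figure 3 table in 4.2.1, which breaks response down by histology. Inclusion criterion 2 in 5.1.2 admits aggressive NHL, including DLBCL, transformed follicular and transformed marginal zone lymphoma, primary mediastinal lymphoma, T-cell and NK/T-cell lymphoma. It excludes indolent B-cell lymphoma. Section 5.3 opens by describing aggressive NHL, but labels both cohorts as aggressive B-cell lymphoma. Of Cohort 1, 8.1 says that "the ORR will be determined for a designated" unirradiated lesion, and 8.2 times this at 3 months.

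**The concern.** With a historical control, the reference rate is the only comparator. It has to describe patients whom the trial would enrol, and the 26% does not: about a third of its patients (10/31) and half of its responders (4/8) come from a histology that is not eligible. A reader of 8.1 takes 35% to be nine points above monotherapy. That gap changes once the excluded patients are removed, and it changes again with the histology considered.

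The cohort labels in 5.3 add a second problem. If Cohort 1 is B-cell only, the 17% in 8.1 is irrelevant. If T-cell lymphoma is included, the labels are wrong. At stake are who may be assigned to Cohort 1 and what an observed rate of 35% can be taken to show about the contribution of radiation.

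**Working it through.** **Step 1: reproduce the plan's own figures.** The table in 4.2.1 gives 8/31 = 25.8% for B-cell and 4/23 = 17.4% for T-cell lymphoma, matching 8.1. In 8.2, the prior Beta(0.35, 0.65) with 7/20 gives a Beta(7.35, 13.65) posterior. Its equal-tailed 90% interval is 0.191 to 0.526, width 0.3346 (stated 0.335). At 10 patients, Pr(OR rate < 0.35) is 0.971 with one response and 0.865 with two, so the boundary of 0-1 is right. The early-stopping probabilities also reproduce. The design arithmetic is not in question.

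**Step 2: is follicular lymphoma ineligible?** Criterion 2 in 5.1.2 excludes indolent B-cell lymphoma and names follicular disease only when transformed. Section 4.2.1 itself counts follicular lymphoma as low grade when it describes the in situ vaccination study (13 of 15 patients). The diagram in 2.2 still carries a line for indolent NHL, but the eligibility text is explicit.

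**Step 3: recompute the reference by histology.** Counts are from the table in 4.2.1; intervals are Clopper-Pearson 95%.

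| Reference group | Responders | Rate | 95% CI |
|---|---|---|---|
| All B-cell, as used in 8.1 | 8/31 | 26% | 12-45% |
| Follicular | 4/10 | 40% | 12-74% |
| B-cell without follicular (DLBCL plus other B-cell) | 4/21 | 19% | 5-42% |
| DLBCL | 4/11 | 36% | 11-69% |
| All T-cell | 4/23 | 17% | 5-39% |

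The 4/21 is (8 - 4)/(31 - 10). It contains ten other B-cell patients with no responders, whose subtypes are not stated, so their match to 5.1.2 is unknown. Of the 23 T-cell patients, 13 had mycosis fungoides; 5.1.2 says only T-cell lymphoma and does not settle whether they match.

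**Step 4: the chance of meeting the OR part with no radiation effect.** Assumption: at least 35% means at least 7/20 overall, after at least 2/10 at the interim look. The posterior mean at 7/20 is 7.35/21 = 0.350, so the observed rate and the posterior mean give the same cut-off. With b(k; 10, p) the binomial probability of k responses in 10,

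P = Σ (k = 2 to 10) b(k; 10, p) × Pr[Bin(10, p) ≥ 7 - k].

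| True rate p | Where it comes from | P |
|---|---|---|
| 0.17 | T-cell rate in 8.1 | 0.040 (4%) |
| 4/21 | B-cell without follicular | 0.068 (7%) |
| 0.26 | B-cell rate in 8.1 | 0.242 (24%) |
| 0.35 | the target itself | 0.576 (58%) |
| 4/11 | DLBCL | 0.625 (63%) |

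The DLT condition is left out. The operating-characteristics table in 8.2 gives early-stopping probabilities and average numbers treated, so it does not show these chances.

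**Step 5: set the eligibility statements side by side.** Aggressive NHL: 5.1.1, the opening of 5.3, 8.1 and the Cohort 1 text of 8.2. T-cell lymphoma named as eligible: 5.1.2. T-cell reference rate given: 8.1. Aggressive B-cell lymphoma only: the two cohort labels in 5.3.

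**Step 6: compare the endpoints.** The table reports response per patient. Cohort 1 scores the unirradiated lesion(s) at 3 months. The reference and the endpoint therefore differ in unit as well as in population.

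**The case against.** The strongest reply has four parts.

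- **The correction helps the sponsor.** Removing the excluded patients lowers the reference from 26% to 19% and makes 35% a harder target. This stands: the follicular error alone does not make the plan lenient.
- **The DLBCL row proves little.** Its interval of 11-69% contains 17%, 19%, 26% and 35%. With one responder fewer it would be 3/11 (27%, CI 6-61%), and the chance in step 4 would fall from 63% to 29%. This also stands. A reader might infer that 35% is a lenient bar, or that the trial would probably be called promising on monotherapy activity alone. The documents do not support that: they give no expected histology mix, do not rank DLBCL above the other eligible types, and offer 11 patients.
- **The histology rows are already printed in 4.2.1.** They are, so nothing is hidden. But 8.1 carries forward only the pooled 26%, without the intervals or the mismatch with 5.1.2.
- **The design tests nothing against 26%.** Correct: 35% is a fixed target with no stated error rate against monotherapy. Even so, 4.2.1 and 8.1 frame the result as improvement over monotherapy, so the comparator should fit the population.

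On T-cell lymphoma, a reader might infer from 5.3 that such patients are barred and that no reference can be fixed. That goes too far. Only the two labels say B-cell, and the surrounding text covers aggressive NHL. It is a wording conflict to be reconciled.

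**Conclusion.** The concern holds in a limited form. The 26% in 8.1 is not a reference for the population that 5.1.2 admits, because half of its responders come from an excluded histology. Without them the B-cell figure is 19% (CI 5-42%), which moves the target from 9 to 16 points above the reference (35 - 26 and 35 - 19). In DLBCL the same table gives 36% (CI 11-69%), so 35% is not clearly above monotherapy there. Neither figure is precise enough to call the target demanding or lenient.

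With no radiation effect, the chance of meeting the OR part runs from 4% at 17% to 63% at 4/11. This rests on the 7/20 reading, on leaving out the DLT condition, and on treating very small subgroup rates as if they were true rates. The upper end depends entirely on 11 patients.

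The consequence is for interpretation and for cohort assignment. Sample size, stopping boundaries, operating characteristics and the 35% threshold are unaffected.

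**What to change.** 1. In 8.1, replace the 26% with the follicular-free reference by histology, with exact 95% CIs and a citation to the table in 4.2.1: DLBCL 4/11 (36%, 11-69%); DLBCL plus other B-cell 4/21 (19%, 5-42%, subtypes not stated); T-cell 4/23 (17%, 5-39%, 13 of them mycosis fungoides). Add that these are patient-level responses, whereas Cohort 1 scores the unirradiated lesion(s) at 3 months.
2. Reconcile the two cohort labels in 5.3 with 5.1.2 and 8.1 on T-cell lymphoma, so that the cohort and its reference cover the same patients.
3. In 8.2, state that reaching 35% does not by itself show improvement over monotherapy. In the analysis plans, add a descriptive report of Cohort 1 response by histology beside the reference.

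The cost is a few sentences in 5.3, 8.1 and 8.2 and one descriptive table. The drawbacks are a more cautious stated interpretation and very small histology subgroups within 20 patients.

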#### **8.2 Statistical Analysis Plan**

Phase II design:

The overall response (OR: complete response + partial response) of non-irradiated lesion(s) at three months and dose limiting toxicity (DLT) at one cycles (3 weeks) will be monitored simultaneously using the Bayesian stopping boundaries calculated based on beta-binomial distributions. Independence is assumed between OR and DLT.

DLT is defined as the following toxicities observed during cycle one of the treatment that are considered by the investigator to be related to therapy:

1. Grade 4 neutropenia (ANC < 500/mm3) lasting more than 7 consecutive days.
2. Grade 3 neutropenia with fever and/or infection, where fever is defined as an oral Temperature  $\geq 38.5^{\circ}\text{C}$ .
3. Grade 4 thrombocytopenia (platelets < 25,000/mm3) lasting more than 7 consecutive Days.
4. Grade 3 thrombocytopenia with clinically significant bleeding.
5. A platelet count < 10,000/mm3 at any time.
6. Grade 3 or greater nausea and/or emesis despite the use of optimal anti-emetic Prophylaxis. Optimal anti-emetic prophylaxis is defined as an anti-emetic regimen that employs a 5-HT3 antagonist given in standard doses and according to standard schedules.
7. Grade 3 or greater diarrhea that occurs despite maximal supportive therapy.
8. Any other Grade 3 or greater non-hematologic toxicity with the following exceptions: Grade 3 arthralgia/myalgia or brief (< 1 week) Grade 3 fatigue.
9. A delay of more than 2 weeks in the initiation of Cycle 2 of treatment because of a lack of adequate recovery of therapy related hematological or non-hematologic toxicities.

In cohort 1 for the patients with multiple sites of aggressive NHL, we will consider that the regimen is promising if the OR rate of the non-irradiated lesion (s) at 3 months is at least 35% and the DLT rate at cycle one is below 30%. A sample size of 20 ensures that, if the trial is not terminated early, a posterior 90% credibility interval for OR rate at 3 months will have width of 0.335 at most, when 7 responses are observed out of the 20 patients, under the assumption of 35% OR rate. The prior probability of OR and DLT for the regimen are modeled by beta distribution ( $\text{Beta}(0.35, 0.65)$  and  $\text{Beta}(0.3, 0.7)$ , respectively). Denoting the probability of OR and DLT by  $\{\theta_{\text{OR}}, \theta_{\text{DLT}}\}$ , and they are compared to fixed targets of OR and DLT rates. The following decision criteria will be applied:

- 1) Stop if  $\text{Prob}\{\theta_{\text{OR}} < 0.35 \mid \text{data}\} > 0.95$ , and
- 2) Stop if  $\text{Prob}\{\theta_{\text{DLT}} > 0.30 \mid \text{data}\} > 0.95$

Patients will be monitored by a cohort size of 10 according to the following stopping boundaries for OR at 3 months and DLT at cycle one. If the number of responses required for moving the trial to next stage has not been achieved, the patient enrollment will be halted until enough responses observed.

Number of patients evaluated	Stop if <= OR observed	Stop if >= DLT observed
10	0-1	6-10
20	Always stop with this many patients	

The operating characteristics are summarized in the following table (based on simulations from 10,000 trials).

True DLT Rate	True OR Rate	Prob (stop the trial early)	Average number of patients treated
0.1	0.15	0.5444	14.56
	0.25	0.2441	17.56
	0.35	0.0861	19.14
	0.45	0.0234	19.77
	0.55	0.0046	19.95
0.2	0.15	0.5472	14.53
	0.25	0.2488	17.51
	0.35	0.0918	19.08
	0.45	0.0295	19.71
	0.55	0.0108	19.89
0.3	0.15	0.5659	14.34
	0.25	0.2798	17.20
	0.35	0.1292	18.71

	0.45	0.0695	19.31
	0.55	0.0516	19.48
0.4	0.15	0.6201	13.80
	0.25	0.3697	16.30
	0.35	0.2379	17.62
	0.45	0.1856	18.14
	0.55	0.1700	18.30
0.5	0.15	0.7161	12.84
	0.25	0.5290	14.71
	0.35	0.4305	15.69
	0.45	0.3914	16.09
	0.55	0.3798	16.20

In cohort 2 patients will be treated to all sites of relapsed or refractory NHL that can be completely included in 1-2 RT field(s), we will consider that the regimen is promising if the OR rate of the radiated disease at 3 months is at least 90% and the DLT rate at cycle one is below 30%. A sample size of 20 ensures that, if the trial is not terminated early, a posterior 90% credibility interval for OR rate at 3 months will have width of 0.203 at most, when 18 responses are observed out of the 20 patients, under the assumption of 90% OR rate. The prior probability of OR and DLT for the regimen are modeled by beta distribution (*Beta*(0.9,0.1) and *Beta*(0.3,0.7), respectively). Denoting the probability of OR and DLT by  $\{\theta_{OR}, \theta_{DLT}\}$ , and they are compared to fixed targets of OR and DLT rates. The following decision criteria will be applied:

- 1) Stop if  $\text{Prob}\{\theta_{OR} < 0.90 \mid \text{data}\} > 0.95$ , and
- 2) Stop if  $\text{Prob}\{\theta_{DLT} > 0.30 \mid \text{data}\} > 0.95$

Patients will be monitored by a cohort size of 10 according to the following stopping boundaries for OR at 3 months and DLT at cycle one. If the number of responses required for

moving the trial to next stage has not been achieved, the patient enrollment will be halted until enough responses observed.

Number of patients evaluated	Stop if <= OR observed	Stop if >= DLT observed
10	0-6	6-10
20	Always stop with this many patients	

The operating characteristics are summarized in the following table (based on simulations from 10,000 trials).

True DLT Rate	True OR Rate	Prob (stop the trial early)	Average number of patients treated
0.1	0.6	0.6178	13.82
	0.7	0.3505	16.50
	0.8	0.1210	18.79
	0.9	0.0129	19.87
	0.95	0.0012	19.99
0.2	0.6	0.6202	13.80
	0.7	0.3545	16.45
	0.8	0.1265	18.74
	0.9	0.0191	19.81
	0.95	0.0074	19.93
0.3	0.6	0.6358	13.64
	0.7	0.3811	16.19
	0.8	0.1625	18.38
	0.9	0.0595	19.40
	0.95	0.0483	19.52

0.4	0.6	0.6813	13.19
	0.7	0.4584	15.42
	0.8	0.2670	17.33
	0.9	0.1769	18.23
	0.95	0.1671	18.33
0.5	0.6	0.7618	12.38
	0.7	0.5953	14.05
	0.8	0.4523	15.48
	0.9	0.3849	16.15
	0.95	0.3776	16.22

The above stopping boundaries and operating characteristics are calculated using MultcLean (v.2.1.0) design software downloaded from <http://biostatistics.mdanderson.org/SoftwareDownload>.

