## 6.0 TRIAL FLOW CHART

## 6.1 Study Flow Chart

Trial Period:	Screening Phase		Pembrolizumab Treatment Cyclesa								End of Treatment	Post-Treatment													
	Treatment Cycle/Title:	Pre-screening (Visit 1)	Main Study Screening (Visit 2)	1	2	3	4	To be repeated up to 16 cycles				Discon	Safety Follow-up	Follow Up Visitsb	Survival Follow-Up										
Scheduling Window (Days) c :		-28 to -1		± 3	± 3	± 3	± 3	± 3	± 3	± 3	At time of Discon	30 days post discon	Every 12 weeks post discon	Every 12 weeks											
HIV 1 and 2 antibody		X																							
CBC with Differential k		X		X	X	X	X	X	X	X		X	X	X											
Comprehensive Serum Chemistry Panel k		X		X	X	X	X	X	X	X		X	X	X											
Urinalysis		X					X					X													
T3, FT4 and TSH		X			X		X		X			X l	X												
Quantitative immunoglobulins: IgG, IgA and IgM		X					X m					X	X												
Bone Marrow Biopsy and Aspirate		X n																							
Efficacy Measurements																									
Chest X Ray, PA and Lateral		X																							
CT Neck, Chest, Abdomen and Pelvis o							X p						X												
PET-CT o		X					X p			X		X q													
Bio-Marker Studies																									
Archival or Newly Obtained Tissue Collection (optional) r		X					X r																		
Correlative Studies Blood Collection (optional) r		X	X	X			X																		
*For patients treated with 22 fractions of EBRT, cycle#2 of pembrolizumab will occur during EBRT																									

a. In general, assessments/procedures are to be performed on Day 1 and prior to the first dose of treatment for each cycle unless otherwise specified. Treatment cycles are 3 weeks (21 days); however the treatment cycle interval may be increased due to toxicity according to the dose modification guidelines provided in Section 5.2.1.2. If the interval is increased, all procedures except for response assessment should be performed based on the new dosing schedule.

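### The numerical DLT rule looks once per cohort, at 10 patients; one added look at 15 under the same prior and threshold is a cheap safety improvement

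*Combined protocol and SAP*

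**What the plan says.** Section 8.2 gives each cohort a maximum of 20 patients and states: "Patients will be monitored by a cohort size of 10 according to the following stopping boundaries". In both cohorts the DLT rate has a Beta(0.3, 0.7) prior, and the cohort stops if the posterior probability that the rate exceeds 0.30 is above 0.95. Each boundary table has one numerical DLT entry, 6 to 10 events among 10 patients. The row for 20 patients reads "Always stop with this many patients". The enrolment halt described with each table depends on responses, not on DLTs.

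The regimen counts as promising in cohort 1 if the three-month response rate "is at least 35% and the DLT rate at cycle one is below 30" per cent, and in cohort 2 if it "is at least 90% and the DLT rate at cycle one is below 30" per cent.

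Outside the rule, section 5.10 item 3 allows early termination on the incidence or severity of adverse drug reactions, and section 7.2.2.3 has the sponsor monitoring aggregated safety data. Neither gives a count or a threshold.

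On the observation window, the monitoring sentence says that "dose limiting toxicity (DLT) at one cycles (3 weeks) will be monitored simultaneously using the Bayesian stopping boundaries". The definition says: "DLT is defined as the following toxicities observed during cycle one of the treatment". Criterion 9 of that definition is "A delay of more than 2 weeks in the initiation of Cycle 2 of treatment" for lack of recovery from toxicity. Footnote a of the section 6.1 flow chart adds: "Treatment cycles are 3 weeks (21 days); however the treatment cycle interval may be increased due to toxicity".

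**The concern.** A cohort can pass the single look with 5 DLTs in 10 and then accumulate events that exceed the plan's own criterion with no look scheduled to act on them. For example, 7 of 12 has posterior probability 0.974 against the 0.95 threshold. What is at stake is exposure: a second group of up to 10 patients is treated with no numerical DLT stop.

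The plan also does not say whether the DLT count at 10 patients is acted on when the DLT window closes or only together with the three-month response.

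The window question is smaller. One event separates 5 of 10 (continue) from 6 of 10 (stop), and whether a criterion 9 event counts depends on how long cycle one is taken to last.

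**Working it through.** **Inputs (section 8.2).** DLT prior Beta(0.3, 0.7); limit 0.30; threshold 0.95; look at 10; maximum 20; response boundaries at 10 patients of 1 or fewer (cohort 1) and 6 or fewer (cohort 2); independence of response and DLT.

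**1. Boundaries.** With x DLTs in n patients the posterior is Beta(0.3 + x, 0.7 + n − x). Pr(rate > 0.30):
- 5/10: 0.890; 6/10: 0.969. The plan's boundary of 6 is reproduced.
- 7/15: 0.900; 8/15: 0.964. A look at 15 would stop at 8 or more.
- 3/5: 0.894; 4/5: 0.984. A look at 5 would stop at 4 or more.
- 9/20: 0.911; 10/20: 0.964. Ten of 20 meets the criterion, but the cohort is then full.

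**2. The plan's operating characteristics.** For a single look at 10, P(stop) = 1 − P(DLT ≤ 5 of 10) × P(response boundary passed), and mean N = 20 − 10 × P(stop). Cohort 1, DLT 0.40, response 0.35: 1 − 0.8338 × 0.9140 = 0.2379, mean N 17.62. Both match the table. All 50 stated stopping probabilities are reproduced to within 0.0001, which confirms one DLT look per cohort.

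**3. DLT rule alone, current design.** P(stop) = P(X ≥ 6 of 10). At 50% DLT this is (210 + 120 + 45 + 10 + 1)/1024 = 386/1024 = 0.377, so 62% pass. At 40% it is 0.166, so 83% pass.

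**4. Adding the look at 15.** The extra stopping is the sum over x = 3, 4, 5 of P(X = x of 10) × P(Y ≥ 8 − x of 5). At 50% DLT: (120 × 1 + 210 × 6 + 252 × 16)/(1024 × 32) = 5412/32768 = 0.165, and 0.377 + 0.165 = 0.542.

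| True DLT rate | 20% | 30% | 40% | 50% | 60% |
|---|---|---|---|---|---|
| P(stop), look at 10 only | 0.6% | 4.7% | 16.6% | 37.7% | 63.3% |
| P(stop), looks at 10 and 15 | 0.9% | 7.1% | 25.4% | 54.2% | 81.1% |
| P(stop), looks at 5, 10 and 15 | 1.3% | 8.4% | 27.4% | 55.9% | 81.9% |

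Mean patients treated at 40%/50%/60%: 18.34/16.23/13.67 now and 17.90/15.40/12.78 with the look at 15. The differences are 0.44, 0.83 and 0.89 patients per cohort. With looks at 5, 10 and 15 the means are 17.23/14.23/10.94, sparing 1.11, 2.00 and 2.73.

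**5. Passing at 10 and finishing with 10 or more of 20.** Sum over x ≤ 5 of P(X = x of 10) × P(Y ≥ 10 − x of 10). At 50% DLT this is 265587/1048576 = 25.3%. It falls to 11.1% with the look at 15 and to 10.5% with looks at 5, 10 and 15.

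**6. With the response rule included.** P(stop) at DLT 30%/40%/50%:
- Cohort 1 at 35% response: from 12.9%/23.8%/43.1% to 15.1%/31.8%/58.2% with the look at 15.
- Cohort 2 at 90% response: from 6.0%/17.7%/38.5% to 8.3%/26.4%/54.8%.

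**7. The promising criterion.** Below 30% is read as 5 or fewer of 20 (assumption: 6/20 = 0.30, and the posterior mean 6.3/21 = 0.30 gives the same cut). The chance of not stopping for DLT and finishing with 5 or fewer is 80.4%/41.6%/12.6%/2.1% at 20%/30%/40%/50% DLT. The look at 15 leaves this unchanged, because a cohort with 8 events cannot finish with 5.

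**8. Criterion 9.** Cycle 2 is due on Day 22 (21-day cycle, footnote a) or Day 23 (footnote r). A delay of more than 14 days is not known until after Day 36 or 37, against a stated window of three weeks.

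**The case against.** The look schedule is disclosed and its operating characteristics are right. The sponsor's own tables show stopping in only 43% of cohort 1 trials at 50% DLT and 35% response, so the limited protection was visible when the design was chosen. That stands, and it is why this is not reported as an error.

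A reader might infer that DLTs in patients 11 to 20 cannot stop enrolment at all. The documents do not support that: sections 5.10 item 3 and 7.2.2.3 leave a judgement-based route, and serious events reach the sponsor within 24 hours (section 7.2.2.1). These routes set no DLT count, so they do not replace the numerical rule.

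A reader might also take 83% and 62% as the share of cohorts that continue. They describe the DLT rule alone. With the response rule, cohort 1 at 35% response continues in 76% and 57% (1 − 0.2379 and 1 − 0.4305). At 25% response it continues in 63% and 47% (1 − 0.3697 and 1 − 0.5290).

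Nor is the conclusion left unprotected. On the reading in step 7, a 50% DLT rate would pass the 30% criterion in about 2% of cohorts.

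The mean saving is modest, and the documents do not suggest that 40% to 60% DLT is expected. Section 4.1.2 reports drug-related serious events in 4.5% of patients in the hematologic monotherapy trial. That is not a DLT rate and involved no protocol EBRT, so it is only indicative.

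On criterion 9, footnote a may let cycle one last until Cycle 2 starts, which would fit the definition though not the three-week figure. If DLTs are reviewed only with the three-month response, such events are known by then.

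**Conclusion.** The point holds as an improvement to consider. The numerical DLT rule has one look per cohort, and DLTs in patients 11 to 20 cannot trigger it. One further look at 15 gives materially better protection at high DLT rates: 16.5 percentage points more stopping at 50% DLT, and fewer than half as many cohorts finishing with 10 or more of 20. It adds 0.3 points of stopping at 20% DLT and 2.4 points at 30%. The problem is reduced, not removed.

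The figures assume independent patients with a constant DLT rate and, as in the plan's tables, no overrun while a window completes. The unchanged chance of meeting the DLT part of the promising criterion rests on the 5-of-20 reading.

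The window mismatch is a real but minor inconsistency. It needs the passages reconciled and does not carry the point.

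**What to change.** Keep the Beta(0.3, 0.7) prior, the 30% limit and the 0.95 threshold. Add one DLT row to both boundary tables: at 15 patients, stop at 8 or more. A row at 5 patients (stop at 4 or more) is optional. State that each DLT count is acted on once that group's DLT window is complete, without waiting for the three-month response. Leave the response look at 10, and restate both operating-characteristics tables.

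Separately, reconcile the three-week figure, the cycle-one definition, criterion 9 and footnote a of section 6.1, and state one counting window. No window length, DLT criterion or clinical rule is proposed here.

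The cost is a SAP amendment, a re-run of the design software and a clarifying sentence. The adverse event data are already reported under section 7.2. The price is slightly more stopping at acceptable DLT rates, and fewer patients for the response estimate in a cohort that stops. If accrual continues while a 3- to 5-week window completes, each look adds about 0.7 to 1.2 patients at the planned 2 per month split equally between cohorts (assumption), or 1.4 to 2.3 if all accrual is in one cohort.
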